1.1 PRIMARY OBJECTIVE

To evaluate the effect of pasireotide LAR on the proportion of patients with clinically non-functioning pituitary adenomas (NFPAs) who achieve treatment response.

1.1.1 End-point for primary objective

Proportion of patients with NFPA who achieve tumor volume reduction of at least 20% after 24-week treatment with pasireotide LAR.

1.2 SECONDARY OBJECTIVES

- To assess the effect of pasireotide LAR on the mean change of tumor volume from baseline to Week 4, 12, 24, 48, 72 and 96.
- To assess the effect of pasireotide LAR on the percentage change of tumor volume from baseline to Week 4, 12, 24, 48, 72 and 96.
- To assess the effect of pasireotide LAR on the proportion of patients achieving tumor volume reduction of at least ≥20% after 4 and 12, 48, 72 and 96 weeks of treatment.
- To assess the effect of pasireotide LAR on the time to tumor response.
- To assess the effect of pasireotide LAR on the disease-related symptoms*
 - *Disease-related symptoms to be evaluated: headache, visual disturbances, fatigue, decreased libido, erectile dysfunction (for males only), irregular or stopped menses (for not post-menopausal female only).
- To evaluate the effect of pasireotide LAR on pituitary function at Weeks 4, 12, 24, 48, 72 and 96.
- To evaluate the effect of pasireotide LAR on alpha subunit levels at Weeks 4, 12, 24, 48, 72 and 96.
- To evaluate the overall safety and tolerability of pasireotide LAR.
- For extension phase: duration of response for patients considered responsive (*i.e.*, patients who achieved a tumor volume reduction of at least 20% with respect the initial tumor volume).
- To assess the percentage of patients that remain with tumor volume stable during the study.

1.2.1 End-points for secondary objectives

The secondary variables are:

Mean change of tumor volume assessed by pituitary MRI from baseline to Week 4, 12, 24, 48, 72 and
 96.

- Percent change of tumor volume assessed by pituitary MRI from baseline to Week 4, 12, 24, 48, 72 and
 96.
- Proportion of patients achieving tumor volume reduction of at least ≥ 20% after 4, 12, 48, 72 and 96 weeks of treatment.
- Time to treatment response for treatment responders, defined as the time from the date of first injection to the first evaluation the patient achieves tumor volume reduction of at least >20%.
- Change from baseline to Week 4, 12, 24, 48, 72 and 96 in disease-related symptoms scores.
- Incidence of pituitary hormonal dysfunction at baseline and at Weeks 4, 12, 24, 48, 72 and 96.
- Proportion of patients achieving alpha subunit reduction of at least 50% at Weeks 4, 12, 24, 48, 72 and 96.
- Proportion of patients achieving normalization of alpha subunit at Weeks 4, 12, 24, 48, 72 and 96.
- Percentage of CTC (≥3) adverse events during treatment with pasireotide LAR.
- Percentage of patients with at least one adverse event with CTC grade ≥ 3.
- Incidence of all adverse events, incidence of laboratory abnormal values and summary of laboratory assessments.
- For extension phase: among patients who had been considered as responsive (*i.e.*, patients who achieved a reduction in tumor volume of at least 20% with respect to the initial tumor volume), assess the number and proportion of patients that remained responsive during the treatment period of extension phase (according to estimates by magnetic resonance at weeks 48, 72 and 96).
- To assess the percentage of patients who remained with tumor volume stable during the study, *i.e.* patients who maintained tumor volume with variation less than 20% with respect to the basal tumor volume (according to evaluations by magnetic resonance imaging at weeks 24, 48, 72 and 96).
- If applicable, assessing whether there was difference in response between patients using dose of 40 and 60 mg of pasireotide LAR.

2 Study design

This is a prospective, multicenter, open-label, single arm, phase II study to evaluate the efficacy and safety of pasireotide LAR in adult patients with NFPA.

Eligible patients will receive pasireotide LAR 60 mg every 28 ± 3 days for 24 weeks, during the Core Phase of the study. The study is complimented by an extension. As per treating physician' discretion, patients who have benefited from the treatment with pasireotide LAR can enter an Extension Phase where they will continue to receive pasireotide LAR 60 mg at 4-week (\pm 3 days) intervals for up to 2 years or until pasireotide or other effective therapy becomes commercially available or until clinical benefit is noted (whichever comes first). Dose reductions to 40 mg will be permitted based on safety issues. In case of rapid deterioration of the visual field or sudden visual loss, the patient will be discontinued from the study.

During the Core Phase of the study, visits will be performed every 28±3 days. There will be two extra visits: Visit 3 and Visit 6.

The design of the study and a schematic of the Core Phase and Extension Phase are presented in **Figure 1** and **Figure 2**, respectively.

Figure 1 Schematic of the Pasireotide LAR Study of NFPA: Core Phase

[figure not shown]
[figure not shown]

Figure 2 Schematic of the Pasireotide LAR Study of NFPA: Core Phase

^{*}Details of efficacy and safety evaluation, presented in Table A1.

3 Population

The population for this study is adult patients with a diagnosis of NFPA who have not undergone any prior therapy (treatment-naïve) for the disease. As tumor volume changes are difficult to be evaluated in microadenomas and also because they may be misdiagnosed with incidentalomas, only patients with macroadenomas (≥ 1 cm) will be included. A total of 23 patients in 10-13 centers will be enrolled in this single-arm open-label study.

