#### 3.2.1 Secondary objective endpoints

The secondary variables are:

- Mean change in tumor volume evaluated by pituitary MRI between baseline and weeks 4, 12, 24, 48, 72, and 96.
- Percent change in tumor volume evaluated by pituitary MRI between baseline and weeks 4, 12, 24, 48, 72, and 96.
- Proportion of patients reaching tumor volume decrease of at least  $\geq$  20% after 4, 12, 48, 72, and 96 weeks of treatment.

- Time to treatment response for treatment responders, defined as the time from the date of the first injection to the first evaluation in which the patient reached a tumor volume decrease of at least ≥ 20%.
- Change in grading score of disease-related symptoms between baseline and weeks 4, 12, 24, 48, 72, and 96.
- Incidence of pituitary hormone dysfunction at baseline and on weeks 4, 12, 24, 48, 72, and 96.
- Proportion of patients reaching alpha subunit decrease of at least 50% on weeks 4, 12, 24, 48, 72, and 96.
- Proportion of patients reaching alpha subunit normalization on weeks 4, 12, 24, 48, 72, and 96.
- Percentage of adverse events with CTC grade  $\geq 3$  during treatment with pasireotide LAR.
- Percentage of patients with at least one adverse event with CTC grade  $\geq 3$ .
- Incidence of all adverse events, incidence of abnormal lab values, and summary of laboratory evaluations.
- For the extension phase: among patients who had been considered as responders (i.e., patients reaching a tumor volume decrease of at least 20% compared to initial tumor volume), to evaluate the number and proportion of patients who remained responsive during the extension phase treatment (according to the magnetic resonance imaging evaluations on weeks 48, 72, and 96).
- To evaluate the percentage of patients remaining with stable tumor volume during the study, i.e., patients who mantained tumor volume variation lower than 20% compared to baseline tumor volume (according to magnetic resonance imaging evaluations on weeks 24, 48, 72, and 96).
- If applicable, to evaluate whether there was a difference in response among patients on 40 and 60 mg doses of pasireotide LAR.

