#### 6.4.5 Early patient discontinuation

#### 6.4.5.1 End of treatment

Patients may withdraw voluntarily from the study or be withdrawn, at the investigator's discretion, at any time. They may be considered as discontinued if they declare their intention to discontinue, or if they do not return for visits, or if they are lost to follow-up for any other reason. Patients may be withdrawn from the study by the investigator for any of the following reasons:

- Acute or progressive vision loss confirmed by a new evaluation of the visual field
- Increased tumor volume defined as tumor volume growth (>20%) and confirmed in a second MRI performed approximately one month later
- Pregnancy
- Adverse event(s)
- Uncontrolled diabetes mellitus
- Clinically significant abnormal laboratory value(s)
- Clinically significant abnormal result(s) of test procedures
- Protocol violation
- Lost to follow-up
- Administrative problems
- Death
- Patients who experience:
- ALT or AST > 3 x ULN and Total Bilirubin  $\ge 2$  x ULN and ALP < 2 x ULN
- ALT or AST > 5 x ULN and  $\le 8$  x persistent ULN for more than 2 weeks
- ALT or AST > 8 x ULN

If any of the discontinuation criteria is met, the study medication must be immediately discontinued. Additionally, appropriate safety follow-up monitoring must be performed, as defined on Section 7.5.2.3. Resuming the study medication after the discontinuation criteria are met is not allowed.

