For the Core Period of the study, efficacy and safety analyses will be conducted on the data collected by the time when all the enrolled patients have completed their EOS Visit. All the formal safety follow-up data of those patients who did not enter the extension study will also be included in the core study safety analyses. A final analysis will be completed when all the patients in the Extension complete their last visit and will be reported in either an additional clinical study report or in an addendum to the core study report.

Other additional data prior to the end of the Core Phase of the trial will be analyzed and then summarized in an additional report of clinical study or in a major study report.

Novartis or designated CRO will analyze all data using the SAS System for data analysis 9.4 . Any data analyses carried out independently by an investigator should be submitted to Novartis before publication or presentation.

The data from all centers participating in the trial will be combined, so that an adequate number of patients will be available for analysis. The statistical analysis methods described in this section will focus on the analysis of the data in the core study. Similar methods will be applied to the analyses in the Extension Phase as appropriate.

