5.5.1 Efficacy variables and analysis

The secondary efficacy endpoints are described in section 1.2.1.

The mean and percent change in tumor volume from baseline to Week 4, 12 and 24 will be presented along with the 90% confidence interval (CI). If data is found to be skewed, CIs for median will also be generated. Incidence rates for patients with \geq 20% reduction in tumor volume and its exact CI will be reported at Week 4 and 12.

Summary statistics will be provided for each disease related symptoms (headaches, visual disturbance, fatigue, symptoms specific to man and woman) at each visits. Change from baseline scores will be also summarized at each visit for all symptoms.

Time to response, defined as time from the first injection to first evaluation where patient achieve tumor volume reduction of at least \geq 20%, will be listed for all patients. If a patient has not achieved tumor response, the time of last assessment will be indicated as censoring time.

Kaplan-Meier analysis will be performed for time to response aiming to compute the median time to response and corresponding 95% confidence interval. Cox regression exploratory analysis will be used to estimate the hazard ratio with corresponding 95% confidence intervals for time to tumor volume reduction of at least \geq 20% as a function of baseline characteristics (duration of disease, dose at V2, dose reduction, visual field (abnormal/normal), and α subunit at V1).

Logistic regression will be performed to explore association between baseline characteristics and tumor response.

Frequency and percentage of patients who present improvement of symptoms related to tumor compression, pituitary hormonal dysfunction, alpha subunit level normalization, will be presented for each symptom at each time point with associated exact 95% CI.

Incidence rates of pituitary hormonal dysfunction, normalization of alpha subunit level and proportion of patients with 50% reduction in alpha subunit level along with its exact 95% CI will be reported at baseline, Week 4, 12 and 24. Analyses for alpha subunit level will be repeated with per protocol population set and for the subgroup of patients with elevated alpha subunit level at baseline.

Hormone profiles, alpha subunit levels and will be summarized at each time point in terms of frequency (N), mean, standard-deviation, median, minimum, and maximum.

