Appendix 2: Statistical Tables – Extension study

Table B 1 - Patients' disposition - extension study

Total (n=xx) Patient agree to be followed for post-treatment evaluations, n (%) No Total Patient agree to be followed for survival, n (%) Yes No Total Primary reason for end of treatment, n (%) Adverse Event(s) Subject withdrew consent Lost to follow-up Administrative problems. Death Disease progression Subject is unable to tolerate the minimum pasireotide LAR dose of 40 mg. Acute or progressive vision loss confirmed by a new visual field evaluation. Uncontrolled diabetes mellitus. Clinically significant abnormal test procedure result(s). Clinically significant abnormal laboratory value(s) Protocol deviation Investigator's decision Other Study populations, n (%) Safety

Table B 2 – Concomitant medication – extension study – FAS population

Table B 2 – Concomitant med	dication – extension study – FAS population	
	Total	
	_(n=xx)	
Any medication or significant nor	ı-drug therapy, n (%)	
Yes		
No		
Total		

Table B 3 – Treatment – extension study – FAS population

	Total (n=xx)					
	V13	V16	V19	V22	V25	Extension phase
Study medication administered, n (%)	-					•
Yes						_
No						_
Total						-
Dose, n (%)						
60 mg						-
40 mg						-
Total						-
Exposure (days) ^{a)}						
N						
Mean						
Median						
Standard Deviation						
Minimum						
Maximum						
Mean administration dose (mg)b)						
N						
Mean						
Median						
Standard Deviation						
Minimum						
Maximum						

a) The difference between the last administration and the first administration of extension phase, in days.
b) Cumulative dose (total dose administered in the extension phase) divided by number administrations (extension phase).

Table B 4 – Magnetic resonance imaging – FAS population

	Total			
	(n=xx)			
	V16	V22	V28	
Volume (cm³)				
N			-	
Mean			-	
Median			-	
Standard Deviation				
Minimum				
Maximum			-	
Tumor is not visible Missing values			-	
iviissing values			-	
Volume change ^{a)} (cm ³)				
N Mean				
Median				
Standard Deviation				
Minimum				
Maximum				
Percentage change in volume ^{a)} (%)				
N				
Mean				
Median				
Standard Deviation				
Minimum				
Maximum				
Reduction of tumor volume ^{b)} , n (%)				
Yes No				
≥20% tumor volume reduction ^{c)} , n (%)				
Yes				
No Total				
Total				
≥20% tumor volume reduction using LOCF method, n (%)				
Yes				
No				
Total				
For patients who achieved a reduction in tumor volume				

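### Stable tumour volume is a declared secondary endpoint, but the SAP gives it no analysis, no table row and no denominator, and no MRI row separates stability from growth of 20% or more

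*SAP*

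**What the plan says.** **The endpoint.** Stable tumour volume is an objective in Protocol 3.2 and SAP 1.2 and an endpoint in Protocol 3.2.1 and SAP 1.2.1. The SAP entry reads "To assess the percentage of patients who remained with tumor volume stable during the study", meaning "patients who maintained tumor volume with variation less than 20% with respect to the basal tumor volume", judged "according to evaluations by magnetic resonance imaging at weeks 24, 48, 72 and 96". The protocol has the same band: "patients who mantained tumor volume variation lower than 20% compared to baseline tumor volume".

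**The analysis text.** On tumour volume, SAP 5.5.1 states: "The mean and percent change in tumor volume from baseline to Week 4, 12 and 24 will be presented". It adds confidence intervals, the rate of reductions of at least 20% at Weeks 4 and 12, time to response, and regression models. Stability is not mentioned there or in Protocol 10.5.1. For later visits, the opening of SAP section 5 says: "Similar methods will be applied to the analyses in the Extension Phase as appropriate".

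**The table shells.** Table 7 (V1, V4, V7, V10) and Table B 4 (V16, V22, V28) show volume, change, percentage change, any reduction yes/no, reduction of at least 20% yes/no, and an LOCF version, labelled in Table B 4 "≥20% tumor volume reduction using LOCF method, n". Table B 4 repeats the 20% reduction row in subsets of patients. One of those subset labels is garbled in the extracted text, but the row beneath it is again a reduction row.

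**Growth.** Protocol 6.4.5.1 lists as a reason for withdrawal: "Increased tumor volume defined as tumor volume growth (>20%) and confirmed in a second MRI performed approximately one month later". Protocol 7.5.7 treats a change of 20% or more in tumour volume as clinically significant.

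**The concern.** The endpoint list and the planned output do not match. A programmer who follows SAP 5.5.1 and fills the shells will produce no stable-volume percentage. If the figure is added later, its denominator, its missing-visit rule and its treatment of responders will be chosen after the volumes are known.

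The result matters to the trial's purpose. Protocol 1.1 says that a therapy able to control tumour growth would be valuable, with shrinkage as a further possibility. At the 10% response rate that the plan calls clinically meaningful, most patients will not be responders. How many of them were stable and how many grew is then a large part of what the trial can report.

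**Working it through.** **1. The plan's own figures.** The documents give no number for stability, so the check starts from the responder figures in SAP 5.6, with n = 19 and p = 0.10:

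P(X ≥ 2) = 1 − 0.9^19 − 19 × 0.1 × 0.9^18 = 1 − 0.1351 − 0.2852 = 0.580, against 58% stated.

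The exact 90% interval for 2/19 is 1.9% to 29.6%, as stated. Both reproduce.

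**2. What the 20% reduction row identifies.** Let R be the number of responders and S the number stable, with no missing scans. Then 0 ≤ S ≤ 19 − R.

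- R = 2: S is 0 to 17, or 0% to 17/19 = 89.5%.
- R = 6: S is 0 to 13, or 0% to 13/19 = 68.4%.

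**3. What the any-reduction row adds, read as titled.** Let A be the number with any reduction. The A − R patients who shrank by less than 20% are certainly stable, so A − R ≤ S ≤ 19 − R. With assumed values A = 10 and R = 2, S is 8 to 17, or 42.1% to 89.5%. The other 9 patients had no change or an increase, and the row cannot say whether it reached 20%.

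**4. What the other summaries add.** If the maximum percentage change at a visit is below 20, nobody grew by 20% and S = 19 − R at that visit. If it is 20 or more, at least one patient grew and the upper limit falls by one (to 16/19 = 84.2% when R = 2). The mean, median and SD constrain the count but do not in general give it. No per-visit summary gives the number stable at all four scans, and Week 24 sits in Table 7 while Weeks 48 to 96 sit in Table B 4.

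**5. Two results that the 20% row cannot tell apart (assumed splits, R = 2).**

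| Split (response / stable / growth) | Stable, exact 90% CI | Growth, exact 90% CI |
|---|---|---|
| 2 / 17 / 0 | 89.5% (70.4 to 98.1) | 0% (0 to 14.6) |
| 2 / 12 / 5 | 63.2% (41.8 to 81.2) | 26.3% (11.0 to 47.6) |

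**6. Denominator.** Extension entry depends on benefit as judged by the physician (Protocol 6.4), and SAP 5.4.3 uses observed data only. Take the second split and assume that the 5 growers do not enter, while the 12 stable patients enter and stay stable. The observed-case figure is 12/14 = 85.7%; on all 19 it is 12/19 = 63.2%.

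**7. Sign of the footnotes.** Footnote a to Tables 7 and B 4 defines change against V1, and footnote b writes it as visit i minus V1. Shrinkage is therefore negative. Footnote b nevertheless codes a reduction when that difference is above 0, and footnote c when the percentage change is at least 20. Taken literally, a tumour at +35% counts as a reduction of at least 20%, and one at −35% does not. Steps 2 to 5 assume that the rows will be programmed as titled.

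**The case against.** The strongest reply is that little is missing. SAP 1.2.1 fixes the band, the baseline and the weeks; SAP 5.5.1 points back to it; SAP 5.5 assigns the FAS; similar methods carry into the extension; and central readers measure the volumes. A sensible programmer could produce the percentage. It is one descriptive secondary endpoint in a proof-of-concept study.

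Much of this stands: no data are lost and the primary endpoint is untouched. But Week 24 is a core time point with no core stability method to carry over, and nothing settles the denominator, missing visits or the place of responders, who fall outside the band.

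Some stronger readings are tempting, and the documents do not support them:

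- *All non-responders fall into one cell.* This is true only of the 20% row. The any-reduction row, as titled, splits them at zero.
- *Growth is counted nowhere.* Tables 1 and B 1 have a Disease progression reason for ending treatment, the maximum percentage change is reported, and SAP 5.5.3.3 lists MRI abnormalities. But the progression row is undefined and misses growth without discontinuation, and a listing is not a count.
- *The result would describe untreated tumours.* Patients are treatment-naïve at entry and all receive pasireotide.
- *Comparing increases with decreases is the only internal check on measurement noise.* The protocol also has a blinded central reader, a 20% threshold chosen with artefact in mind, and a repeat MRI to confirm growth. Such a comparison would also mix noise with true growth and drug effect.
- *Protocol Table 1-4 predicts the number of growing tumours.* Its 0% to 25% would be 0 to 4.75 of 19, but it concerns another drug, over 1 to 12 months, with no growth threshold stated; the 25% is 2 of 8 patients. It is illustrative only.
- *Section 2 of the protocol makes growth control the aim in these patients.* It ties growth control to the time after surgery, and prior pituitary surgery is excluded here. Protocol 1.1 is more general.

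**Conclusion.** The point holds in this form: a declared secondary endpoint has a definition but no analysis, table row or denominator, and the MRI tables do not separate a small increase from growth of 20% or more. With 2 responders in 19, the 20% reduction row allows any stable proportion from 0% to 89.5%. The any-reduction row raises the lower limit, and the maximum percentage change settles a single visit only when it is below 20.

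These bounds assume 19 patients with complete scans and rows programmed as titled. The splits in steps 3, 5 and 6 are assumed. The matter should be settled before analysis, because the choice of denominator alone can move the stable percentage materially. It does not threaten the primary analysis.

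**What to change.** 1. Keep the existing rows for reduction of at least 20% and for LOCF. Correct footnotes b and c in Tables 7 and B 4 so that a reduction is a negative change (visit i minus V1).
2. Add to both tables, at each MRI, three exclusive categories against V1: decrease of at least 20%, change within 20%, increase of at least 20%. Give a missing count and an exact CI, at whichever level the SAP finally adopts (its sample-size tables use 90%, its section 7 says 95%).
3. Add one row for stable at every scheduled assessment (Weeks 24, 48, 72 and 96) and one for stable or response, so that responders are not read as failures of stability.
4. State the denominators in SAP 5.5.1. Report Week 24 on the FAS with a baseline MRI. Report Weeks 48 to 96 both among extension entrants and among all treated patients. Count patients withdrawn for tumour growth as not stable rather than dropping them under the observed-case rule, and show other absent scans as missing.

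The cost is a paragraph of SAP text and a few extra programmed rows. No new assessment is needed.
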